### **Study Drugs or Devices**

Dermabond Prineo is a product that is already available at New York Presbyterian Hospital, and has been used regularly by our gynecologic oncology colleagues for skin closure after cesarean hysterectomy. In services will be performed by the Dermabond Ethicon team via in- person or video training on Labor and Delivery for the surgical team and nursing staff, followed by distribution of the product in the L&D operating rooms. The in-services will serve to familiarize the surgical teams and clinical staff on the appropriate use and application of Dermabond Prineo at time of cesarean skin closure, as well as postpartum aftercare as described above for the postpartum clinical staff. Postoperative patient education will be individualized according to the type of skin closure patients receive; postoperative surgical dressings will be removed on POD2-3 for standard subcuticular skin closure, versus at 7-14 days for the Dermabond Prineo group.

## **Study Questionnaires**

The Patient Scar Assessment Scale (POSAS) is a patient questionnaire that has been validated in prior studies, including in the dermatologic and plastics literature [11, 15-18]. PSAS includes assessment of scar related pain, itchiness, color, stiffness, thickness, and irregularity (ranked 1-10 w/ 1 representing normal skin). This survey will be administered via telehealth video visits at a 4-6 week postoperative research visit, as previously described in “Procedures”. A copy of these questionnaires can be found at the end of this protocol.

## **Potential Risks**

Given that the study is not introducing new medications or treatments, there are no additional significant risks anticipated to patients enrolled in the study except for the presumed baseline risk to all patients during cesarean delivery, which includes but is not limited to risk of bleeding, infection, injury to surrounding organs, and wound complications, such as wound infection, separation, hematoma, or fascial dehiscence.. In all cases, obstetric providers will take standard precautions to minimize surgical site infection (SSI). As part of routine post-delivery care, all patients will have vital signs, urine output, blood count, and symptoms monitored closely after delivery to quickly identify and treat patients with SSI or wound infection.

As discussed previously, standard perioperative interventions as part of the perioperative bundle to prevent and decrease the incidence of cesarean section SSIs will be utilized for all patients in the study, including the use of chlorhexidine skin prep, hair removal around the surgical site, preoperative antibiotic administration for surgical prophylaxis, strict glycemic control, vaginal prep for laboring patients, and subcutaneous skin closure with suture for subcutaneous depth of more than 2cm. These interventions have been demonstrated in prior studies to effectively decrease the incidence of cesarean section SSI [3], and remain the standard of care at our institution. These precautions will continue to be applied during our study.

For both randomization groups, routine postoperative care to decrease cesarean section SSI will also continue to be utilized, including patient and postpartum nursing education on appropriate wound care. Patients who receive standard subcuticular skin closure will have their surgical dressings removed on POD2-3 and will be encouraged to shower following dressing removal, as is the current standard of care at our institution. Patients who receive Dermabond Prineo skin closure will keep the Dermabond mesh in place until day 7-14, or until the mesh falls off on its own. Every attempt will be made to keep the incision clean and dry for both study groups, and any postoperative SSI or wound infection will be treated with wound exploration and/or antibiotics, as deemed clinically appropriate.

As previously described, an interim analysis may be conducted once the study is underway to ensure that there is not a disproportionate incidence of the primary composite outcome or other adverse outcome in the Dermabond Prineo group, although this has not been shown in any prior studies involving this skin closure method. Although unlikely, it is possible that participating in this study may involve risks to the patient that are not expected. No neonatal risks are anticipated as part of this study, as the intervention will occur following delivery.

## **Potential Benefits**

If patients decide to participate in this research study, they may or may not directly benefit from their participation. However, if the patient is randomized to Dermabond Prineo closure, they may potentially benefit from increased satisfaction with their cesarean incision. Patients randomized to the Dermabond Prineo group may also potentially benefit from secondary outcomes, such as decreased incidence of SSI, skin closure and overall operative time, lower postoperative pain scores, and higher observer and patient satisfaction scores.

In addition, the data gathered on the above primary and secondary outcomes will serve to increase the general knowledge base regarding the use of tissue adhesives at time of cesarean section skin closure, and subsequently benefit patients and clinicians in the future.

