### **Objective**

The primary outcome of the current study is to assess patient satisfaction with cesarean scar cosmesis when comparing standard subcuticular suture closure to the Dermabond Prineo tissue adhesive system. This outcome will be assessed with the validated Patient Scar Assessment Scale

(PSAS) [7]. This questionnaire has previously been used in the skin staples versus suture obstetric literature [8].

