### **Study Design**

This will be a prospective randomized, open label trial as both surgeons and patients will know what type of closure technique is utilized. Two study groups will be defined as described above. In group 1, Dermabond Prineo will be utilized in place of standard subcuticular closure at the time of cesarean skin closure. In group 2, standard subcuticular closure will be utilized at the time of cesarean skin closure. All patients will be randomized immediately preoperatively as part of the multidisciplinary preoperative briefing process. See procedure below for further details.

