## Procedures

Permission from primary teams will be sought on Columbia University Medical Center: New York Presbyterian – Children’s Hospital of New York (CHONY) labor and delivery and informed consent obtained from women willing to participate in the study. Women scheduled for cesarean delivery will be contacted by the research team via 1 of 3 options: 1) via telephone to obtain telephone consent in the week prior to their scheduled procedure; 2) in person at the last outpatient visit prior to their scheduled c-section; 3) in person at the time of admission to labor and delivery for their scheduled procedure if they cannot be contacted beforehand. Women admitted to the antepartum service or labor and delivery for induction of labor or spontaneous labor who then undergo intrapartum cesarean delivery will be consented at the time the decision is made to proceed with cesarean.

Once consent is obtained, randomization will be performed using a computer-generated algorithm. Consenting women will be randomly assigned in a 1:1 ratio to each group by trained research personnel. Women meeting inclusion criteria will be randomized to two groups: 1) experimental arm: Dermabond Prineo skin closure at the time of cesarean section; or 2) control arm: standard subcuticular skin closure at the time of cesarean section. Following randomization, the assigned intervention will be announced to the surgical team at the time of the surgical time-out in the operating room, dictating either standard subcuticular skin closure or closure with Dermabond Prineo, both of which will be available in the Labor and Delivery operating rooms. Those who receive standard subcuticular skin closure will have their incision covered by a standard pressure dressing, as per routine protocol. Those who receive Dermabond Prineo will forego the application of an additional pressure dressing, as one of the benefits of the Dermabond Prineo closure is that an overlying dressing is no longer necessary. Thus, this is an open label trial as both the surgical team and the patient will be able to visualize what type of closure technique was utilized.

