In terms of immediate postoperative wound assessment on postoperative day 3, a member of the surgical team will perform a standard postoperative wound assessment prior to hospital discharge to assess for evidence of the wound complications, including the presence or absence of superficial SSI, deep SSI, endometritis, and/or wound disruption. Postoperative pain scores are also documented for all patients by postpartum nursing staff as part of routine postoperative care, and will be assessed for patients in both groups.

Long term postoperative follow up will then be assessed by the research team at 4-6 week postoperative follow up visits. Patients will be consented, at the time of initial consent to the study, to a short telehealth video or telephone visit at 4-6 weeks postoperative. This research visit will administer the Patient Scar Assessment Scale (PSAS) questionnaire to assess for our primary outcome of patient scar satisfaction. Additionally, chart review will be performed at this time to assess for the presence of other secondary outcomes, such as wound complication.

The research team will perform chart review to abstract maternal demographics, delivery information, and maternal and neonatal outcomes from maternal and neonatal medical records. This information will be entered into REDCap, a web-based data collection system. Once the study is underway, an interim analysis using the previously described statistical methodology may be appropriate to ensure that there is not a disproportionate incidence of the primary composite outcome or other adverse outcome in the experimental group.

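### In an open-label trial with a patient-rated primary outcome, Potential Benefits names a better result for the Prineo arm only; equipoise wording and one shared scar message would remove an avoidable source of expectation bias

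*Combined protocol and SAP*

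**What the plan says.** **No blinding.** Study Design describes a "prospective randomized, open label trial as both surgeons and patients will know what type of closure technique is utilized". Procedures repeats this and gives the reason: the closure is visible.

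**Patient-rated primary outcome.** The Objective is to "assess patient satisfaction with cesarean scar cosmesis when comparing standard subcuticular suture closure to the Dermabond Prineo tissue adhesive system", using the PSAS. Under Study Questionnaires, "PSAS includes assessment of scar related pain, itchiness, color, stiffness, thickness, and irregularity (ranked 1-10 w/ 1 representing normal skin". Procedures has the research team administer it at a "short telehealth video or telephone visit at 4-6 weeks postoperative".

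**Benefit wording.** Potential Benefits opens with a general statement that participants may gain nothing directly. It continues: "if the patient is randomized to Dermabond Prineo closure, they may potentially benefit from increased satisfaction with their cesarean incision". The next sentence lists further possible gains for the Prineo group, including fewer surgical site infections, shorter closure and operative times, lower pain scores and higher satisfaction scores. Nothing is listed for the suture group.

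**Teaching.** Study Drugs or Devices says that "In services will be performed by the Dermabond Ethicon team", for the surgical team and nursing staff. Their stated purpose is correct use and application, plus aftercare. The same section says that "Postoperative patient education will be individualized according to the type of skin closure patients receive"; the content it gives is when the dressing or mesh comes off. Potential Risks adds wound-care education for patients and postpartum nurses in both groups.

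**Equipoise elsewhere.** Primary Research Question / Hypothesis poses better scar satisfaction as an open question. Anticipated Budget says that the product cannot be endorsed until it is shown to be safe and no worse than suture.

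**The concern.** Open label is a reasonable choice here because the two closures look different. It does leave a patient-rated outcome exposed to what patients expect. One protection remains under the investigators' control: telling both arms the same thing about the result to be expected.

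Potential Benefits departs from that. It presents the quantity being measured as a possible gain of one arm. If the wording reaches patients through consent or recruitment material, Prineo patients may expect a better scar, and suture patients may feel that they missed one. A PSAS difference would then mix any real effect on the scar with the effect of the message. Analysis after enrollment cannot separate the two, because message and treatment coincide.

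The protocol describes no common message on expected scar appearance, no measure of expectation, no masked administration of the PSAS and no sensitivity analysis for this bias.

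**Working it through.** **Inputs from Sample Size Calculation**
- Suture mean 20, SD 6 in both arms
- Effect: 20% relative reduction
- Two-sided alpha 0.05, power 80%
- Loss to follow-up 20%
- 94 per arm, 188 in total

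**Assumed input.** The bias b is the shift in mean PSAS due to expectation alone. The documents give no value, so a range is shown.

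**1. Planned effect.** 0.20 × 20 = 4 points, from 20 to 16. Over six items this is 4/6 = 0.67 points per item.

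**2. The plan's sample size.** The normal formula gives n = 2 × (1.96 + 0.84)² × 6² / 4² = 35.3, so 36 per arm; a t-test needs 37. Dividing by 0.8 gives 45 to 47 per arm, or 90 to 94 in total. The stated 188 is about twice this and is not reproduced. That is a separate matter. The steps below use the planned 94 per arm.

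**3. Precision at the planned size.** Evaluable per arm: 94 × 0.8 = 75. SE = 6 × √(2/75) = 0.98. The smallest observed difference that reaches p<0.05 is about 1.9 points (t critical value × SE), or 1.9/6 = 0.32 per item. That is 48% of the planned effect.

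**4. Chance of p<0.05 with no true effect.** On the normal approximation this is P(Z > 1.96 − b/SE) + P(Z < −1.96 − b/SE). For b = 1, b/SE = 1.02 and the sum is 0.174 + 0.001 = 0.175. The noncentral t distribution gives:

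| Assumed bias, points (per item) | Chance of p<0.05 |
|---|---|
| 0 | 5% |
| 0.5 (0.08) | 8% |
| 1 (0.17) | 17% |
| 1.5 (0.25) | 33% |
| 2 (0.33) | 53% |

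**5. Dependence on trial size.** At 37 evaluable per arm, the number that the stated inputs require, a 2-point bias gives 29% instead of 53%. A larger trial does not protect against bias; it makes a given bias more likely to reach significance.

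**6. The text side by side.** The hypothesis asks whether Prineo gives better scar satisfaction. Potential Benefits offers that result as a possible gain of Prineo. The hedged wording and the opening disclaimer soften this, but the disclaimer concerns participation in general and the named gains all belong to one arm.

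**The case against.** The case against has real force on several points.

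- **The design is disclosed.** The trial claims no blind, so none can fail. This stands.
- **The manufacturer trains staff, not patients.** A reader might infer that the manufacturer educates participants. The text has it teaching surgical and nursing staff, with application and aftercare as the stated scope. The sentence on patient education is separate and names no provider. Influence through trained staff is possible, but only as an inference.
- **The suture arm is not left without education.** A reader might infer this from the Prineo in-services. Potential Risks gives wound-care education to both groups, and Study Drugs or Devices gives dressing-removal instructions for suture patients.
- **The benefit wording is hedged and sits in a protocol.** It is not a patient script, and the consent pages were not available. Neither a one-sided message to patients nor the lack of a neutral one can therefore be asserted.
- **The size is assumed.** The PSAS asks about six specific features, not only overall satisfaction, and nothing in the documents quantifies an expectation effect.
- **The remedy is partial.** Patients will still know whether they received the new product or the standard one.

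What remains is narrow: the protocol's own benefit statement favors one arm on the primary outcome, and it describes no safeguard for an unblinded patient rating. Specific items such as color, stiffness or itch are still subjective. A partial remedy is worthwhile when it costs almost nothing.

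**Conclusion.** The point holds as a low-cost improvement to wording, not as a flaw that invalidates the trial. Potential Benefits names the primary outcome, infection and pain as possible gains of Prineo alone, in a trial where patients know their arm and rate the outcome themselves. If patients receive that message, it adds a difference in expectation that could have been avoided.

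The documents do not give the size of the bias. The figures of 8%, 17% and 53% for assumed shifts of 0.5, 1 and 2 points show how sensitive the test is. They rest on SD 6, 75 evaluable per arm, a t-test and no true effect. A reader might infer that expectation could account for much of the planned 4 points. The calculation does not show this; it shows only that a shift well below 4 points could reach significance.

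The conclusion also depends on the consent and recruitment material following the protocol wording, which could not be checked.

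**What to change.** 1. Reword Potential Benefits to say that it is not known whether either closure gives a better scar, fewer complications or less pain. Make the same change in any consent or recruitment script that follows it.
2. Add to the patient education in Study Drugs or Devices and Potential Risks one short message, identical in both arms, on scar appearance and healing to be expected at 4-6 weeks, with no comparative claims. Leave the arm-specific aftercare instructions as they are.
3. When the PSAS result is reported, acknowledge that residual open-label bias remains.

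The cost is a minor IRB amendment and an edit to the patient handout. No extra patients or visits are needed. The change reduces differences in expectation but cannot remove them, because patients will still know their closure.

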## **Alternatives**

The alternative to this study is to not participate in the study, and to continue receiving standard intraoperative and postoperative care.

## **Data and Safety Monitoring**

Data will be stored in a secured REDCAP database and only accessed on a password protected computer. We will abide by the OBGYN departmental data safety and monitoring policy. The data will be used only by those investigators involved in the study. The data will not be shared with other researchers. The data will not become a part of the subjects' permanent record. Once all of the data abstraction is complete and before data is ready for analysis, the REDCAP Manager will remove all identifiers from the file and send the coded file to the data analysts. This study will be monitored in accordance with the Department of OBGYN Quality Assurance Monitoring standard operating procedure.

Detailed information concerning adverse events (AEs) will be collected by research personnel and evaluated throughout the trial (including enrollment through the 6 week follow up period). All adverse events will be causally assessed by the Principal Investigator and reported per the CUMC HRPO policy of reporting Adverse events.

<https://research.columbia.edu/sites/default/files/content/HRPO/Unanticipated%20Problems%20Policy.FINAL%20VERSION.012408.pdf>

## **Feasibility/Timeline**

There are approximately 30 cesarean deliveries per week at our institution. Assuming that 90% meet eligibility criteria, and assuming that 50% of patients agree to participate in the study, we will be able to recruit 1-2 patients per day. Thus, recruitment and enrollment will take approximately 4-6 months to reach the expected sample size of 188 patients.

## **Anticipated Budget**

This goal of this proposal is to secure a charitable donation from Ethicon for 94 Dermabond Prineo units for use in this study as the experimental arm. The results of this study will aim to promote this product as an alternative to cesarean skin closure, and to increase its routine use at Columbia University Medical Center for our high volume obstetric practice. We cannot promote or endorse the use of this product until it has been shown to be a safe and non-inferior alternative to our current standard of skin closure with skin sutures at the time of cesarean delivery. Thus, we will need a donation of the Dermabond Prineo product in order to meet this goal.

